6.1.4 Definitions

6.1.4.1 Baseline (Core)

For de novo subjects, the baseline (core) is undefined. For other subjects, the baseline (core) is defined as follows.

For effectiveness endpoints (excluding seizure), the baseline (core) will be defined dependent on their core study. For subjects from ZX008-1501, ZX008-1502, or ZX008-1504 Cohort 2, baseline (core) is the last value prior to randomization in the preceding double-blind study. For subjects from ZX008-1504 Cohort 1, baseline (core) is the last value prior to the start of PK dosing and assessments. For De Novo subjects, the baseline is the last value prior to dosing in ZX008-1503.

For all subjects in Study ZX008-1501, Study ZX008-1502, or Study ZX008-1504 Cohort 2, the baseline (core) period is equivalent to the core study pre-randomization period, i.e., the approximately 42-day span just prior to randomization and start of treatment in the core study. The baseline (core) seizure frequency will be based on the information collected from their daily diaries during the baseline period (lasting approximately 42 days).

For subjects from Study ZX008-1504 Cohort 1 the baseline (core) for efficacy rating scales (e.g. questionnaires) will be the last rating prior to start of dosing in the Core Study. Baseline seizure frequency for Study ZX008-1504 Cohort 1 will not be calculated.

6.1.4.2 *Baseline (OLE)*

Baseline (OLE) value for the Open-label treatment period is defined as the last assessment on or before the start of the OLE period. In most cases, (though not seizure frequency) this will be the value obtained at Visit 1 (Study Day 1) of Study ZX008-1503.

Thus, Baseline (OLE) lab, vital signs, ECG, ECHO, assessments refer to the assessments obtained on this day, as does Baseline (OLE) value for effectiveness endpoints with the exception of seizures.

For de novo subjects, the baseline (OLE) seizure frequency will be based on the information collected from their daily diaries during the baseline period (lasting approximately 28 days) prior to first dose in ZX008-1503.

6.1.4.3 *Open-Label Extension (OLE) Treatment Period*

The OLE Treatment Period covers the 36 months during which subjects will receive open label treatment with ZX008.

For each subject, OLE day 1 (OLED1) is the subject's first day of dosing in the OLE period. Study day for 1503 begins with OLED1.

6.1.4.4 *Post-dosing Period*

The Post-dosing Period begins immediately at the end of OLE Treatment Period and extends for 2 weeks.

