Pre-OLE Phase	Baseline (OLE) Period – de novo subjects	This description here applies to the de novo subjects. This start date of this period be the date of screening. The end date of the period will be the last date prior to the first dose of study drug in Study ZX008-1503.
OLE Phase	OLE Treatment Period	The OLE Treatment Period consists of the 36-month period from Visit 1 of the OLE study through Visit 16 of the OLE study The OLE Treatment Period start date is the date of first dose in Study ZX008-1503. The OLE Treatment Period end date is the date of end of study visit, Visit 16/ET. For subjects who discontinue early from the study, the OLE Treatment Period end date will be the date of the ET visit - safety measures collected at the last clinic visit will be used even in the event that study drug was discontinued prior to the date of the visit. Note: Adverse events occurring up to Visit 17 are regarded as occurring during treatment. In addition, AEs occurring up to 30 days after the last dose date will be regarding as treatment emergent.
OLE Phase	Taper Period	The Taper period consists of 2 weeks starting from end of study/early termination visit (Visit 16) + 1 day. The end date of this period is the date recorded for Visit 17.
Post-OLE Phase	Post-OLE Period	The start date of the post-OLE period is the date of Visit 17, + 1 day for subjects who complete the OLE Treatment period, or the day after the date of end of taper, for subjects who discontinue early. [There is not explicit end date for the post-OLE Phase. However, if needed, this may be set to be 45 days after the date of Visit 19, or V17 date + 210.]

For the purpose of statistical analysis, visit windows around the target visit dates will be implemented to capture effectiveness and/or safety data within similar periods. These windows are distinct from the

permissible visit scheduling windows specified in the Visit Schedule in the protocol that are used for the conduct of the study.

The following rules will be used to window data into treatment periods for tabulations that are generated by time during the OLE Treatment period.

Table 7a. Time Intervals for Analysis Visits for Seizure Analysis*

Analysis Phase/Period	Scheduled Visit Number in ZX008-1503	Analysis Visit**	Time Interval (label on output)	Time Interval (Day)
Pre-OLE	N/A	-99	Baseline (Core)*	Core Study Day -42 to Day-1 of Core Study
Pre-OLE	N/A	-9	Core Study (T+M)*	Day 1 of Core Study to End of T+M in Core Study

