Pre-OLE	N/A	-1	Core Study Final * Week	End of T+M in Core Study – 6 days, to End of T+M in Core Study
Pre-OLE de novo	N/A	-99	Baseline (OLE)*	Day -28 to Day -1 of Study ZX008-1503
OLE	3	1	Month 1 (OLE)	1-30
OLE	4	2	Month 2 (OLE)	31-60
OLE	5	3	Month 3 (OLE)	61-90
OLE	6	4	Month 4-6 (OLE)	91-180
OLE	7	5	Month 7-9 (OLE)	181-270
OLE	8	6	Month 10-12 (OLE)	271-360
OLE	9	7	Month 13-15 (OLE)	361-450
OLE	10	8	Month 16-18 (OLE)	451-540
OLE	11	9	Month 19-21 (OLE)	541-630
OLE	12	10	Month 22-24 (OLE)	631-730
OLE	13	11	Month 25-27 (OLE)	731-820
OLE	14	12	Month 28-30 (OLE)	821-910
OLE	15	13	Month 31-33 (OLE)	911-1000
OLE	16	14	Month 34-36 (OLE)	1001-1095
OLE	NA	99	Month 01-EOS (ENDPT1)	1 to min(Last Dose date, Visit 16 date)
OLE	NA	98	Month 02-EOS (ENDPT2)	31 to min(Last Dose date, Visit 16 date)

Note: EOS/ET date = Visit 16 date. Per protocol, Visit 17 is end of the OLE Phase.

T+M=Titration + Maintenance in Core Study.

*Subjects in Study ZX008-1504 Cohort 1 will not have a baseline(core), For those subjects, the Core Study(T+M) represents all their seizure data during the transition period in the core study. Their core study final week will be the last 7 days of seizure data prior to the first visit in ZX008-1503. De novo subjects start Study ZX008-1503 treatment after a screening period.

**Analysis visit numbers are not the same as nominal visit numbers.

Table 7b. Time Intervals for Questionnaires*

Analysis Phase/Period	Scheduled Visit Number in ZX008-1503	Analysis Visit Number*	Time Interval (label on output)	Time Interval (Day)	Target Time Point (Day)
Pre-OLE	N/A	-99	Baseline (Core)	<1	Core Study Day -42 to Day-1 of Core Study
Pre-OLE	1	1	Baseline (OLE)	1	1
OLE	3	3	Month 1 (OLE)	21 to 44	30
OLE	4	4	Month 2 (OLE)	45 to 74	60
OLE	5	5	Month 3 (OLE)	75 to 134	90
OLE	6	6	Month 6 (OLE)	135 to 224	180
OLE	7	7	Month 9 (OLE)	225 to 314	270
OLE	8	8	Month 12 (OLE)	315 to 409	365
OLE	9	9	Month 15 (OLE)	410 to 499	455
OLE	10	10	Month 18 (OLE)	500 to 589	545
OLE	11	11	Month 21 (OLE)	590 to 679	635
OLE	12	12	Month 24 (OLE)	680 to 774	730
OLE	13	13	Month 27 (OLE)	775 to 864	820
OLE	14	14	Month 30 (OLE)	865 to 954	910
OLE	15	15	Month 33 (OLE)	955 to 1044	1000
OLE	16	16	Month 36 (OLE)	1045 to 1109	1095
OLE	OLE Last Visit**	99	Last Value	Day 2 to Visit 17 date	

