6.3.2.8 Duration of Prolonged Seizures

Duration of convulsive seizures at baseline and on treatment will be presented by treatment group and overall using categories as <2 min, 2-10 min and >10 min.

To obtain a baseline probability distribution for the three categories, we will proceed as follows: For each subject, we will calculate the percentage of their total number of baseline seizures that is in each category. (For example, if the subject had 5 seizures, with 2 in the first category and 3 in the last category, their percentage distribution would be 40%, 0%, and 60% in the <2, 2-10, and >10 categories. We can calculate similar numbers for the next subject, and so on.) We will then average these over all subjects to obtain the percentage of subjects' seizures that were <2 min in duration, the percentage between 2-10 min in duration, and the percentage >10 min in duration. These 3 percentages should total 100%. Thus, we will obtain a distribution of seizure duration for baseline.

Using the seizure duration data obtained for the OLE period, we will proceed similarly, to obtain a distribution for the OLE period.

No formal analytic method will be used to assess the distribution of seizure duration during baseline vs. during the OLE treatment period. However, it is expected that the distribution may shift in such a way that a greater proportion of seizures during the OLE period will have shorter interval duration when compared to the baseline period.

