95% Exact CI	(xx.x%,xx.x%)	(xx.x%,xx.x%)	(xx.x%,xx.x%)	(xx.x%,xx.x%)	(xx.x%,xx.x%)	(xx.x%,xx.x%)
Total unique events: SE as an AE, plus seizures >10 min						
Unique events						
1	XX (XX.X%)	XX (XX.X%)	XX (XX.X%)	XX (XX.X%)	XX (XX.X%)	XX (XX.X%)
2	XX (XX.X%)	XX (XX.X%)	XX (XX.X%)	XX (XX.X%)	XX (XX.X%)	XX (XX.X%)
3	XX (XX.X%)	XX (XX.X%)	XX (XX.X%)	XX (XX.X%)	XX (XX.X%)	XX (XX.X%)
.....						

mITT = Intent-to-treat;

[1] Any AE with Status Epilepticus or presumed Epilepticus

[2] This includes all single seizures >10 minutes in duration as recorded in the subject's seizure diary. For each subject, the number of episodes is calculated; then the number per subject for each treatment group is obtained by summing across subjects in each group and dividing by number of subjects in that treatment group who had single seizures > 10 min.

Programming note: Use the same Table 14.2.9.1 shell for

Table 14.2.9.1.1
Number of episodes of status epilepticus (SE)
mITT Population (Japan)

Table 14.2.9.2
Duration of Seizures
mITT Population

Percentage of seizures by duration	PBO-ZX008 OL (N = XX)	ZX 0.2 – ZX008 OL (N = XX)	ZX 0.5 – ZX008 OL (N = XX)	ZX 0.8 – ZX008 OL (N = XX)	ZX008 OL (N = XX)	De Novo Subjects (N = XX)
Baseline						
<2 min	XX.XX	XX.XX	XX.XX	XX.XX	XX.XX	NA
2-10 min	XX.XX	XX.XX	XX.XX	XX.XX	XX.XX	NA
>10 min	XX.XX	XX.XX	XX.XX	XX.XX	XX.XX	NA
OLE Treatment Period						
<2 min	XX.XX	XX.XX	XX.XX	XX.XX	XX.XX	XX.XX
2-10 min	XX.XX	XX.XX	XX.XX	XX.XX	XX.XX	XX.XX
>10 min	XX.XX	XX.XX	XX.XX	XX.XX	XX.XX	XX.XX

mITT = modified Intent-to-treat; 95% CI are based on the exact (Clopper-Pearson) method. NA = Not Applicable.

Programming notes:

To calculate the probability of a seizure <2 min. for a given treatment group, for each subject, calculate the proportion of seizures < 2 min. For example, if the subject has a total of 5 seizures with 2 being <2 min in duration, their proportion is 2/5. Add these proportions for all subjects in the treatment group, and divide the total by the number of subjects to get the treatment group proportion of subjects with seizure duration <2 min. Then multiply the result by 100 to get the percentage.

Repeat for the other treatment groups. Repeat for seizure durations 2-10 min., and for >10 min.

Table 14.2.10.1
 Clinical Global Impression of Improvement, Parent/Caregiver Rating
 mITT Population

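### The seizure-duration shell marks the de novo baseline as not applicable, although the SAP defines a pre-dose diary baseline for these subjects and uses it in its seizure-frequency tables

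*SAP*

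**What the plan says.** Section 6.3.2.8 of the SAP sets the analysis: "Duration of convulsive seizures at baseline and on treatment will be presented by treatment group and overall". Each subject's seizures are split into three duration categories, the percentages are averaged over subjects, and the baseline distribution is set beside the OLE distribution. The comparison is descriptive: "No formal analytic method will be used to assess the distribution of seizure duration during baseline vs. during the OLE treatment period". No exception is made for de novo subjects.

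Shell Table 14.2.9.2 implements this. Its De Novo column has NA in all three baseline rows, with the footnote "NA = Not Applicable", and result placeholders in all three OLE rows.

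Three places define a seizure baseline for de novo subjects:

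- Section 6.1.4.2, on the value against which their later seizure counts are judged: "will be based on the information collected from their daily diaries during the baseline period (lasting approximately 28 days) prior to first dose in ZX008-1503".
- Table 6: a Baseline (OLE) Period that starts at screening, and "The end date of the period will be the last date prior to the first dose of study drug in Study ZX008-1503".
- Table 7a (windows for seizure analysis): "Day -28 to Day -1 of Study ZX008-1503".

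Against this, section 6.3.1.2 states that all seizure analyses take Baseline (Core) as their baseline, and section 6.1.4.1 states that this baseline is undefined for de novo subjects.

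**The concern.** The purpose of Table 14.2.9.2 is to show whether seizures become shorter on open-label treatment. With the baseline cells fixed as NA, the de novo column reports an OLE distribution and nothing to read it against, beside columns that do have a reference. A programmer who follows the shell will leave pre-dose diary data unused, and the report will describe a comparison as inapplicable when the plan supplies the window for it.

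This baseline is also of some interest in its own right. It lies directly before the first open-label dose, whereas the baseline of subjects from the double-blind core studies precedes a whole period of blinded treatment.

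**Working it through.** No sample-size, power or error-rate figure is involved, so the check sets the texts side by side.

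**1. The cells.** De Novo column of Table 14.2.9.2: 3 of 3 baseline cells are NA and 3 of 3 OLE cells are to be filled. A before/after shift cannot be read from it.

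**2. Is there a baseline window?** Yes. Table 7a covers seizure analysis in general and gives the de novo window the analysis visit code -99, the same code as Baseline (Core).

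**3. Does the diary record duration?** Yes. Section 6.3.2.7 and footnote [2] of Table 14.2.9.1 take seizures longer than 10 minutes from the seizure diary, and Listing 16.2.6.1 (diary data) has a duration column.

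**4. How do other seizure outputs treat de novo subjects?**

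| Place | De novo baseline |
|---|---|
| Table 14.2.1.1.1 (convulsive seizure frequency) | 28 days before dosing; change computed from it |
| Table 14.2.1.1.3, footnote [1] | 28 days before dosing |
| Table 14.2.6.1 (non-convulsive seizure frequency) | 28 days before dosing; change computed from it |
| Section 6.3.2.3 (responders) | Separate de novo estimate and response curve, which need a baseline |
| Table 14.2.2.1 (responders) | De novo column filled, but the footnote defines only the core-study baseline |
| Table 14.2.9.2 (duration) | NA |

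**5. Can the rule in section 6.3.1.2 account for the NA?** Read literally with section 6.1.4.1, yes. Applied consistently, it would also empty the de novo change-from-baseline cells of Tables 14.2.1.1.1 and 14.2.6.1 and rule out the de novo responder analysis. The SAP plans all of these, so it does not follow the rule for this group.

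**6. Size.** The shells' group table gives about 35 de novo subjects; Table 1 gives TBD. Subjects from Study 1504 Cohort 1 have no seizure baseline and should not count in the denominator. Table 1 gives 320 for Groups 1-4, and the shells' table gives 360 - 40 = 320. The de novo share is then 35 / (320 + 35) = 9.9% of subjects who could have a baseline duration distribution.

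**The case against.** The strongest defence is that NA follows from the text: section 6.3.1.2 prescribes Baseline (Core) for every seizure analysis, and de novo subjects have none. The real conflict would then lie between that sentence and the frequency shells. This stands as an explanation of how the NA arose, and it means that filling three cells is not a sufficient repair. It does not stand as a justification, because the SAP sets the rule aside for de novo subjects wherever it reports their change in seizure frequency.

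Second, section 6.1.4.2 words the 28-day baseline for seizure frequency, not duration. That is correct. Extending it rests on the general scope of Table 7a and on the diary recording duration.

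Third, section 6.3.2.8 does not name de novo subjects, whereas sections 6.3.2.3, 6.3.2.4, 6.3.3.1 and 6.3.3.3 do. But Table 1 lists them as Group 10, and the duration shell gives them a column, so they are within the planned table.

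Fourth, the NA is not a lone slip. Sections 6.3.2.5 and 6.3.2.9 also word their baselines as the core-study one. This is a reason to correct the rule at its source.

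Finally, the matter is small: a descriptive, secondary display in a small group, with the de novo before/after comparison kept in the frequency tables. That stands and sets the weight of the point.

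**Conclusion.** The point holds as an internal inconsistency of minor weight. Table 14.2.9.2 labels as not applicable a baseline that the SAP defines and uses elsewhere, and the planned baseline-versus-OLE description of seizure duration is lost for about 35 subjects. The primary safety objective is unaffected. The conclusion assumes that the pre-dose diary captured duration as the on-treatment diary does, and that the approximate count of 35 is near the final number.

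Three stronger readings are tempting and are not supported:

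- A reader might multiply 35 subjects by the entry minimum of 4 convulsive seizures per 4 weeks and infer that at least 35 × 4 = 140 baseline seizures go unused. That criterion (Table 4, footnote b) covers the 12 weeks before screening and rests on parent report or medical notes, so it sets no minimum for the diary window. Screening lasts up to 28 days and may be shorter.
- A reader might call the window drug-free. ZX008 is adjunctive, and de novo subjects may be taking stiripentol. The window is free of ZX008 only.
- A reader might infer that the repair costs nothing because the data and window exist. Section 6.3.1.2 and Listing 16.2.6.1 also need to be aligned.

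**What to change.** 1. In Table 14.2.9.2, replace the three NA entries in the De Novo baseline rows with the distribution from the Day -28 to Day -1 diary (Table 7a), and drop the NA abbreviation from the footnote.
2. Add the de novo baseline footnote used in Table 14.2.6.1.
3. Amend the sentence in section 6.3.1.2 so that Baseline (OLE) is the seizure baseline for de novo subjects and Baseline (Core) remains the baseline for subjects from the double-blind core studies.
4. Add a Baseline (OLE) period to Listing 16.2.6.1, which now offers only the core baseline, the core T+M period and OLE treatment. The Japan listing 16.2.6.1.1 uses the same shell and would inherit the change.

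If duration was not captured in the pre-dose diary, keep the cells empty and state that reason in the footnote.

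The cost is a few shell and text edits and minor programming. Table 14.2.9.2 is not marked in Appendix 1 for the interim analysis, the 120-day update or the Japan report, so changing that table alters no output flagged for those deliveries.

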2.2 SECONDARY OBJECTIVES

The secondary objectives of the study are:

- To assess the effect of ZX008 relative to the pre-ZX008 baseline on the following effectiveness measures:
 - The change in the frequency of convulsive seizures.

- The proportion of subjects who achieve a $\geq 25\%$, $\geq 50\%$, and $\geq 75\%$ reduction in convulsive seizure frequency.
- The duration of the longest interval between convulsive seizures.
- The percentage of convulsive seizure-free days.
- The change in the frequency of non-convulsive seizures.
- The change in the frequency of convulsive + non-convulsive seizures.
- To estimate the incidence of the following on subjects receiving ZX008:
 - Use of rescue medication
 - Hospitalization to treat seizures
 - Status epilepticus
- To assess the effect of ZX0008 relative to the pre-ZX0008 baseline on the following measures:
 - Quality of Life in Childhood Epilepsy (QOLCE) score
 - The Pediatric Quality of Life Inventory (PedsQL) (Version 4.0) – Parent Report
 - PedsQL Family Impact Module (Version 2.0) – Parent Report – mITT Population
 - QoL of the parent/care giver using the EQ-5D-5L scale
 - Affective symptoms of the parent/caregiver using the HADS.
- To assess the effect of ZX0008 on the following global ratings
 - Clinical Global Impression – Improvement rating, as assessed by the principal investigator
 - Clinical Global Impression – Improvement rating, as assessed by the parent/caregiver

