3.2 TREATMENTS

Subjects in the double-blind studies Z008-1501, -1502, and cohort 2 of 1504 who enter Study ZX008-1503 would have transitioned to 0.2 mg/kg during the transition period (between Visits 12 and 13), as described in the 1501 and 1502 Clinical Study Protocols Section 5.5.5, and 1504 Sections 5.5.6 and 5.5.7. Subjects entering from Cohort 1 in Study ZX008-1504 will enter a transition period at a fixed dose of ZX008 0.2 mg/kg/day for up to 24 additional weeks.

In Study ZX008-1503, during the OLE Treatment Period, all subjects will be treated initially with 0.2 mg/kg/day for 1 month to assess effectiveness of this dose in all study subjects. After 1 month at a dose of 0.2 mg/kg/day, the investigator may adjust the dose of each subject based on effectiveness and tolerability. Subjects whose condition worsened relative to their status at the end of the double-blind feeder study could request permission to increase to 0.4 mg/kg/day (max 30mg) after approximately 2 weeks on the 0.2 mg/kg dose. Dose changes should be made in increments of 0.2 mg/kg/day, to a maximum of 0.8 mg/kg/day but not to exceed total dose of 30 mg/day. Dose increases should not occur earlier than every 14 days at each dose level. For subjects in Study ZX008-1504 Cohort 2, the dose titration schedule is 0.2 mg/kg/day, to 0.4, to 0.5 not to exceed 20 mg/day. Dose increases may only occur after a review of the diary and reported AEs, and if, in the investigator's opinion, seizure frequency, severity, and/or duration indicates a change in medication regimen is warranted. Dose decreases for tolerability can occur at the investigator's discretion, in dose amounts and frequency appropriate for the situation. ZX008 dose adjustments outside of these parameters should be discussed with the Medical Monitor prior to initiation.

Effectiveness and safety data will be provided for all subjects treated with ZX008. Data will be summarized by subjects' treatment group in their previous study.

The treatment groups that may be used to summarize the results of the final analysis are presented in Table 1. Groups 1 to 5 are the basic treatment groups.

Table 1. Treatment Groups in Study ZX008-1503 According to Treatment in Feeder Study

Name of Treatment Group	Treatment Group Code	AED Treatment from Feeder study	Feeder Study(s)	Approximate Total Number of subjects at Final Analysis

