AED=antiepileptic drug; BMI=body mass index; BRIEF=Behavior Rating Inventory of Executive Function; C=Collect; CBD=cannabidiol; CGI-I=Clinical Global Impression-Improvement; D=Dispense; ECG=electrocardiogram; EOS=end of study; ET=early termination; EQ-5D-5L=standardized measure of health status; HADS=Hospital Anxiety and Depression Scale; PedsQL=Pediatric Quality of Life Inventory; QoL=quality of life; QOLCE=Quality of Life in Childhood Epilepsy; R=Review

NOTE: If a subject has a birthday during the study that makes a previously unrequired assessment now required (eg, Tanner staging in a male subject who turns 8 years old during the study), this assessment(s) should be initiated at visits subsequent to the birthday.

**** de Novo subjects are subjects who did not participate in one of the core studies and may or may not be currently taking STP.**

- a: For subjects enrolling from one of the core studies use data collected at Visit 12 and Visit 13 of Study ZX008-1501 or ZX008-1502.
For de novo subjects, a screening period up to 28 days is required. During this period, informed consent is required prior to any study-related procedures. All results to determine eligibility must be reviewed prior to receiving the first dose of study medication at Visit 1.
For all subjects, clinical laboratory results and all ECHO/ECG results must be available and meet eligibility criteria prior to receiving the first dose of study medication at Visit 1.
- b: De Novo subjects must meet entry criteria 3 to 7, and 10, including having had ≥ 4 convulsive seizures (tonic, tonic-atonic, tonic-clonic, clonic) per 4-week period for past 12 weeks prior to screening, by parent/guardian report to investigator or investigator medical notes.
- c: At the discretion of the investigator, Visit 2 may be conducted as a phone visit.
- d: Or early termination.
- e: Follow-up ECG, ECHO, and physical examination will be performed 3 and 6 months after study completion or early termination.
- f: For subjects enrolling from one of the core studies, use core study Visit 12 information unless complete neurological examination is warranted based on significant changes in subject status.
- g: ECHOs will be performed at Months 1, 3, 6, 9, 12, 15, 18, 21, 24, 27, 30, and 33.

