6.1.2 Multiplicity Issues

This is an open-label extension study with no formal comparisons to be made between treatment groups defined by subjects' initial regimen in the previous study. Comparisons will be made within each treatment group comparing measurements observed during different time points in the OLE to the measurements obtained during the baseline period in the double-blind or PK study completed prior to this OLE.

Confidence intervals presented for descriptive purposes only will each have nominal 95% coverage probability.

No formal adjustment for multiplicity is made.

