Overall Quality of Life*		Average of 16 subscale scores*

*For each subject, an Overall Quality of Life Score will be computed by adding each subscale score for each individual and then dividing by 16.

Individual subject data for the domains will be listed.

For each subscale, descriptive statistics will be provided for the baseline, EOS/ET, and change from baseline subscale mean, overall, by treatment group and for de novo subjects.

For each treatment group at Baseline and End of Study/ET, the mean and standard deviation of the subscale score will be presented for each QOLCE subscale and for the Overall Quality of Life score.

In addition, the change from baseline in the Overall QOL score will be calculated for each subject by subtracting the baseline overall score from the overall score measured at End of Study/ET. The change from baseline for each treatment group will be summarized using the mean and standard deviation. Statistical significance of the within group change from baseline will be assessed using a Wilcoxon signed rank test.

Individual subject data for the subscales will be listed.

6.3.3.4 *Quality of Life of the Parent/Caregiver using EQ-5D-5L Scale*

The impact on the quality of life of the parent/caregiver responsible for a patient with DS will be assessed at Baseline (Core Study) and during the OLE Treatment period using the EQ-5D-5L.

The EQ-5D-5L health questionnaire is a health-related quality of life instrument with five dimensions: mobility, self-care, usual activities, pain/discomfort, and anxiety/depression. Each dimension has five possible levels: no problems, slight problems, moderate problems, severe problems and extreme problems.

The summary of results will follow the EQ-5D-5L guideline results presentation. For the “Health Profiles” descriptive system summary results will show the number, and percentage of subjects in each Item score (No Problems, Slight Problems, Moderate Problem, Severe Problem, Extreme Problems) overall and by treatment group, at baseline (Core), during the OLE treatment period and at EOS/ET. In addition, the item scores will be classified into two categories as “No Problems” and “Problems” comprised of items: slight, moderate, severe and extreme problems. Summary results will show number of patients and percentage with “No Problems” and with “Problems” overall, by treatment group and for de novo subjects, at baseline, during OLE Treatment period, and at EOS/ET.

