Clinical Global Impression of Improvement, Investigator Rating
mITT Population (Japan)

Programming note: Use shell for Figure 14.2..10.2 shell to produce the following.

Figure 14.2.10.4
Clinical Global Impression of Improvement, Investigator Rating
mITT Population

Figure 14.2.10.4.1
Clinical Global Impression of Improvement, Investigator Rating
mITT Population (Japan)

Table 14.2.11.1
 Quality of Life in Childhood Epilepsy (QOLCE)
 mITT Population

Domain	Subscale	Visit	Statistics	PBO-ZX008 OL (N = XX)	ZX 0.2 – ZX008 OL (N = XX)	ZX 0.5 – ZX008 OL (N = XX)	ZX 0.8 – ZX008 OL (N = XX)	ZX008 OL (N = XXX)	De Novo Subjects (N = XX)
Physical	Physical Restriction	OLE Baseline (Visit 1)	n	XX	XX	XX	XX	XX	XX
			Mean (SD)	XX (XX.X)	XX (XX.X)	XX (XX.X)	XX (XX.X)	XX (XX.X)	XX (XX.X)
		OLE Month 1 (Visit 3)	n	XX	XX	XX	XX	XX	XX
			Mean (SD)	XX (XX.X)	XX (XX.X)	XX (XX.X)	XX (XX.X)	XX (XX.X)	XX (XX.X)
		OLE Month 1 Chg BL	n	XX	XX	XX	XX	XX	XX
			Mean (SD)	XX (XX.X)	XX (XX.X)	XX (XX.X)	XX (XX.X)	XX (XX.X)	XX (XX.X)
			Continue for OLE Month 2 (Visit 4) OLE Month 3 (Visit 5) OLE Month 6 (Visit 6) OLE Month 9 (Visit 7) OLE Month 12 (Visit 8) OLE Month 15 (Visit 9) OLE Month 18 (Visit 10) OLE Month 21 (Visit 11) OLE Month 24 (Visit 12) OLE Month 27 (Visit 13) OLE Month 30 (Visit 14) OLE Month 33 (Visit 15) OLE EOS/EOT (Visit 16)						

TLF Shells

Zogenix International Limited
ZX008-1503

		EOS/EOT							
REPEAT FOR									
Physical	Physical Restrictions								
Physical	Energy/Fatigue								
Well-being	Depression								
Well-being	Anxiety								
Well-being	Control/helplessness								
Well-being	Self-esteem								
Cognition	Attention/Concentration								
Cognition	Memory								
Cognition	Language								
Cognition	Other Cognitive								
Social Activities	Social Interactions								
Social Activities	Social Activities								
Social Activities	Stigma Item								
Behavior	Behavior								
General Health	General Health Item								
Quality of Life	Quality of life Item								

TLF Shells

Zogenix International Limited
ZX008-1503

Overall Quality of Life	Overall Quality of Life	OLE Baseline (Visit 1)	n	XX	XX	XX	XX	XX	XX
			Mean (SD)	XX (XX.X)	XX (XX.X)	XX (XX.X)	XX (XX.X)	XX (XX.X)	XX (XX.X)
		OLE Month 1 (Visit 3)	n	XX	XX	XX	XX	XX	XX
			Mean (SD)	XX (XX.X)	XX (XX.X)	XX (XX.X)	XX (XX.X)	XX (XX.X)	XX (XX.X)
		OLE Month 1 Chg BL	n	XX	XX	XX	XX	XX	XX
			Mean (SD)	XX (XX.X)	XX (XX.X)	XX (XX.X)	XX (XX.X)	XX (XX.X)	XX (XX.X)
			P-value*	0.xxx	0.xxx	0.xxx	0.xxx	0.xxx	0.xxx

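### The SAP text points to the pre-ZX008 core baseline for the quality-of-life and caregiver scales, but the table shells show only the OLE Visit 1 baseline and leave the change-from-baseline rows undefined

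*SAP*

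**What the plan says.** **Objective and SAP text**

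- Section 2.2 introduces the list of quality-of-life and caregiver scales with: "To assess the effect of ZX0008 relative to the pre-ZX0008 baseline on the following measures".
- Section 6.1.2 says OLE time points are compared, within group, with "measurements obtained during the baseline period in the double-blind or PK study completed prior to this OLE".
- Section 6.1.4.1, for non-seizure effectiveness endpoints in subjects from 1501, 1502 or 1504 Cohort 2: "baseline (core) is the last value prior to randomization in the preceding double-blind study". For 1504 Cohort 1 it is the last rating before core-study dosing.
- Table 7b, which sets the questionnaire windows, has a Baseline (Core) row as well as a Baseline (OLE) row.
- Section 6.3.3.3 (QOLCE) places baseline in the core study. Section 6.3.3.4 says the caregiver's quality of life "will be assessed at Baseline (Core Study) and during the OLE Treatment period using the EQ-5D-5L", and it names Baseline (Core) again for the VAS.
- Sections 6.3.3.5 (HADS), 6.3.3.6 (PedsQL 4.0) and 6.3.3.7 (Family Impact Module) say only baseline, unqualified.

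**Shells**

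- Tables 14.2.11.1, 14.2.12.1-2, 14.2.13.1-3 and 14.2.14.1-2 show "OLE Baseline (Visit 1" as the baseline row. The one exception is an unqualified Baseline in the Self-care block of Table 14.2.13.1. None has a Baseline (Core) row.

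**What the Visit 1 value is**

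- Section 6.1.4.2 on Baseline (OLE): "In most cases, (though not seizure frequency) this will be the value obtained at Visit 1 (Study Day 1) of Study ZX008-1503".
- Table 4, footnote a: "For subjects enrolling from one of the core studies use data collected at Visit 12 and Visit 13 of Study ZX008-1501 or ZX008-1502". Table 5, footnote a, gives the same visits for 1504 Cohort 2 and the last transition visit for Cohort 1.
- Section 3.2: subjects rolling over from the double-blind studies "would have transitioned to 0.2 mg/kg during the transition period (between Visits 12 and 13").

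**The concern.** Two parts of one document give different reference points for the same endpoints. Change from a core-study, pre-treatment rating describes what happened after ZX008 was started. Change from OLE Visit 1 describes, for a subject from an active arm, only whether an on-drug rating was maintained. Benefit or harm that arose in the core study would be subtracted out.

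The pooled ZX008 OL column would also mix reference states: on-drug ratings for the active arms, and ratings taken at or near the end of placebo treatment for the former placebo arm. The Wilcoxon signed-rank p-values would test that mixed contrast. As an assumed illustration only: a group that gained 8 points in the core study and 2 more in the OLE would be shown as +2, where the objective asks for 8 + 2 = +10.

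**Working it through.** **1. Which shells report change.**

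| Table | Scale | Change row | Wilcoxon p-value shown |
|---|---|---|---|
| 14.2.11.1 | QOLCE | yes | Overall score only |
| 14.2.12.1 | PedsQL 4.0 | yes | yes |
| 14.2.12.2 | Family Impact Module | yes | summary and total scores only |
| 14.2.13.1, 14.2.13.2 | EQ-5D-5L profile | no (category counts) | no |
| 14.2.13.3 | EQ-5D-5L VAS | yes | yes |
| 14.2.14.1 | HADS categories | no (category counts) | no |
| 14.2.14.2 | HADS scores | yes | yes |

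Five of the eight tables report change. In the other three the discrepancy is confined to the baseline row.

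**2. What change from baseline means in those five.** No footnote in them defines BL. The only labelled baseline is OLE Visit 1, so that is the natural reading, though it is an inference from layout. The convulsive seizure shell, Table 14.2.1.1.1, shows how it can be settled: its footnote ties baseline to the period before double-blind treatment, with a separate rule for de novo subjects.

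**3. How many roll-over subjects had ZX008 before OLE Visit 1.** The inputs are the approximate counts in Table 1 (Section 3.2): Group 1 = 120, Group 2 = 80, Group 3 = 80, Group 4 = 40, Group 5 = 18.

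- Groups 2-5: 80 + 80 + 40 + 18 = 218, matching the SAP's Group 8.
- Groups 1-5: 120 + 218 = 338, matching the SAP's Group 9.
- Share by feeder assignment alone: 218/338 = 64.5%.
- With the counts in the TFL shells (240 of 360): 66.7%.
- Double-blind roll-overs only (Groups 2-4 of Groups 1-4): 200/320 = 62.5%.
- If former placebo subjects are also counted, because they moved to 0.2 mg/kg between Visits 12 and 13: 338/338 = 100%.

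The SAP does not say whether Visit 12 or Visit 13 supplies the questionnaires. For former placebo subjects a Visit 12 rating would precede ZX008 and a Visit 13 rating would not. The 64.5% is therefore a minimum on the Table 1 counts.

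**4. HADS separately.** The footnote to Table 14.2.14.1 leaves out subjects from 1504, so 218/338 is the wrong ratio there. Groups 2 and 3 come only from 1501 and 1502: 80 + 80 = 160. Table 1 does not split placebo by study, but placebo subjects from those two studies cannot exceed 120. The share is then at least 160/(160 + 120) = 57.1%.

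**5. De novo subjects.** Section 6.1.4.1 calls their Baseline (Core) undefined and takes their baseline as the last value before dosing in 1503. Their OLE baseline is pre-ZX008, so their column already fits the objective. The TFL group table keeps them outside the pooled ZX008 OL column.

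**The case against.** The strongest reply is that the SAP text already fixes the intended contrast. Sections 6.1.2 and 6.1.4.1, Table 7b, and the QOLCE and EQ-5D-5L sections all point to the core baseline, and nothing in the document says that a shell overrides the text. Some of these shells refer back to the SAP for scoring. That stands: a reader might infer that the sponsor has chosen the OLE baseline and that the secondary objective will certainly go unanswered, and the SAP does not establish either. What it shows is a contradiction, with a baseline left unspecified for HADS and PedsQL beyond the general rules.

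It does not dispose of the point. For HADS and PedsQL the shell is the only scale-specific wording. If Chg BL was meant as change from core, the shells omit the baseline values behind every reported change and p-value. Section 6.1.4.2 also defines a Baseline (OLE) for non-seizure effectiveness endpoints, so two defined baselines compete and the tables must say which applies.

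It is also fair that these are secondary scales in an open-label study whose primary objective is safety, and that Section 6.1.1 asks for caution with within-group changes. That lowers the severity. A descriptive summary must still describe the stated quantity.

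**Conclusion.** The SAP contradicts itself on the baseline for these scales. If the five change tables are programmed as laid out, their active-arm and pooled columns would report change from a value taken after core-study treatment. On the Table 1 counts that affects at least 64.5% of roll-over subjects (at least 57.1% for HADS). This rests on reading the undefined change rows against the only labelled baseline, and on Table 1's approximate numbers.

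Three wider readings are not supported. The three category-count tables contain no change or test. The de novo column is not affected. Former placebo subjects cannot be called either treated or untreated at this baseline without knowing which core visit supplied the rating.

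Severity: should be fixed before the final report. In Appendix 1 none of these tables is marked for the interim analysis, the 120-day update or the Japan report, so no listed interim output depends on them.

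**What to change.** 1. Add a Baseline (Core) row for core-study subjects to Tables 14.2.11.1, 14.2.12.1-2, 14.2.13.1-3 and 14.2.14.1-2.
2. In Tables 14.2.11.1, 14.2.12.1-2, 14.2.13.3 and 14.2.14.2, add a footnote defining the change, and its Wilcoxon test where shown, as change from Baseline (Core) for core-study subjects. That is the last pre-randomisation value or, for 1504 Cohort 1 where the scale is reported for them, the last value before core-study dosing. For de novo subjects, define it as change from Baseline (OLE), the last pre-dose value.
3. Keep the OLE Visit 1 row as descriptive for roll-over subjects. It remains the reference for de novo subjects.
4. Name the same baseline in Sections 6.3.3.5, 6.3.3.6 and 6.3.3.7, and correct the unqualified label in the Self-care block of Table 14.2.13.1.

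The cost is an edit to the shells and to three short sections. It uses core-study ratings that the SAP already plans to use, and no new data collection.
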